3.5 Analysis sets

3.5.1 Enrolled Set (ES)

The Enrolled Set (ES) consists of all study participants who sign the Informed Consent Form.

This analysis set includes screening failures and will be used for the summary of disposition of study participants and for selected data listings (which will include all available data for the screening failures).

3.5.2 Safety Analysis Set (SS)

The Safety Analysis Set (SS) consists of all study participants who receive at least 1 full or partial dose of study treatment.

This analysis set will be used for the reporting of demographic, Baseline, safety and immunogenicity data. All summaries of the exploratory antitumor activity endpoints will be repeated for the SS as a sensitivity analysis.

3.5.3 Per-protocol Set (PPS)

The Per-protocol Set (PPS) consists of all study participants in the SS who do not have IPDs that may substantially affect antitumor activity. Potential exclusions will be reviewed at the DEMs and a final determination of the composition of this analysis set will be made prior to the final database lock for Part A.

The PPS will be the primary analysis set for the analysis of the exploratory antitumor activity endpoints.

3.5.4 Pharmacokinetic Set (PKS)

The Pharmacokinetic Set (PKS) consists of all study participants in the SS who have at least 1 evaluable postdose UCB6114 concentration sample (i.e. a sample which is above the lower limit of quantitation and for which the date and time of the sample and prior date and time of dosing are known). Additional participants or specific samples may be excluded from the PKS at the discretion of the Advanced Modeling and Simulation scientist/Quantitative Clinical Pharmacologist at UCB.

Pharmacokinetic analysis will be performed for the PKS.

3.5.5 Anti-drug Antibody Set (ADAS)

The Anti-drug Antibody Set (ADAS) consists of all study participants in the SS who have at least 1 evaluable ADA assessment.

Immunogenicity analyses will be performed for the ADAS.

3.5.6 Pharmacodynamic Set (PDS)

The Pharmacodynamic Set (PDS) consists of all study participants in the SS who have at least 1 evaluable PD assessment (where appropriate, the sample should be above the lower limit of quantitation and the date and time of the sample should be known).

Pharmacodynamic analysis will be performed for the PDS.

3.5.7 DLT Evaluable Set (DES)

The DLT Evaluable Set (DES) will include all study participants who, during the 28-day DLT Observation Period, receive the planned dose of UCB6114.

The DES will be used only for evaluations by the SMC for dose-escalation decisions.

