During the Treatment Period, UCB6114 will be administered as monotherapy by iv infusion on Days 1 and 15 of each cycle, until the occurrence of progressive disease, unacceptable toxicity, or participant withdrawal. Dosing levels will be escalated (or de-escalated) stepwise in successive cohorts of 3 to 6 evaluable participants using a modified rolling-6 design until the recommended Phase 2 dose for monotherapy (RP2D-M) is determined. The rolling-6 design is an algorithm-based design in which a total of 6 participants can be enrolled at the same dose level. The modification requires that each dose level incorporates a sentinel participant. The enrollment of a sentinel participant in each cohort has been included as an additional risk mitigation measure to monitor infusion-related reactions and other early onset study treatment-related AEs. Each sentinel participant will be assessed for at least 24 hours following the second treatment administration on Day 15 of Cycle 1 before further participants within the dose cohort can be enrolled. In the absence of a DLT observation in the sentinel participant after 16 days, the remaining 5 participants may be enrolled concurrently (see Figure 4-1 in the protocol). Should the sentinel participant experience a DLT, then participants 2 and 3 will be enrolled and observed for 16 days (see Figure 4-2 in the protocol).

Part A of the study is planned to be conducted at 6 study sites in the United Kingdom (UK).

A schematic diagram of Part A of the study is provided in Figure 2-1.

Figure 2-1: Study Schematic for Part A

d=days; iv=intravenous; Q2W=every 2 weeks; SMC=safety monitoring committee.

Dose escalation to the next cohort can be performed when 3/3, 4/4, 5/5, 5/6, or 6/6 participants have completed the DLT observation period and have not experienced a DLT. When a single DLT has been observed in a given dose level, participants will be included at the same dose level, up to a total of 6 participants. De-escalation will occur when 2 or more participants experience a DLT at a dose level and when less than 6 participants have been evaluated at the dose level below the level at which 2 DLTs occurred. Dose escalation requires at least 3

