participants to be treated and observed for at least 28 days after the first dose (assuming UCB6114 is dosed every 2 weeks [Q2W]). If dosing is less frequent (due to missed or delayed doses or due to a planned change in schedule), at least 3 participants should be treated and observed for a minimum of 28 days (i.e. 1 cycle), before dose escalation is considered.

The final decision for dose escalation in the next cohort will be made by a Safety Monitoring Committee (SMC) taking into account all the observed safety and tolerability data, and the PK and PD and ADA profile (where available) of the dose in that cohort and also of the doses in all previous cohorts, as relevant (for further details on the SMC, please refer to [Section 4.5](#)).

Eligible participants who withdraw from the study before receiving study treatment will be replaced. Participants who fail to receive the second planned dose of UCB6114 within 7 days of the scheduled dose administration day, during the DLT observation period, for reasons not related to toxicity, will also be replaced for the purpose of DLT assessment. Safety data for replaced participants will be included in the data listings and in the summary tables, as applicable.

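### Section 3.5.7 defines the DLT Evaluable Set by receipt of the planned dose alone, so on its most natural reading a DLT that stops dosing takes the participant out of the set, against Section 2.3

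*SAP*

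**What the plan says.** Part A SAP, Section 3.5.7, defines the set: "The DLT Evaluable Set (DES) will include all study participants who, during the 28-day DLT Observation Period, receive the planned dose of UCB6114". It gives the set a single purpose: "The DES will be used only for evaluations by the SMC for dose-escalation decisions". Section 3.5.7 of the Part A1 SAP has the same definition, there for SMC decisions on whether a dosing schedule and the module can go on.

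Part A Section 2.3 holds the rules that the set serves:

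- Escalation: "Dose escalation to the next cohort can be performed when 3/3, 4/4, 5/5, 5/6, or 6/6 participants have completed the DLT observation period", and have had no DLT.
- One DLT: "When a single DLT has been observed in a given dose level, participants will be included at the same dose level", to a total of 6.
- Two or more: "De-escalation will occur when 2 or more participants experience a DLT at a dose level", provided that fewer than 6 have been evaluated at the level below.
- Replacement: a participant whose second dose is not given within 7 days of its scheduled day, "for reasons not related to toxicity, will also be replaced for the purpose of DLT assessment".

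Section 2.3 describes cohorts of 3 to 6 evaluable participants. The DES is the only definition of DLT-evaluable in the document.

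**The concern.** A DLT-evaluable set normally has two routes in: enough exposure and follow-up without a DLT, or a DLT at any point after dosing starts. Section 3.5.7 has only the first route, and without the follow-up condition that Section 2.3 attaches to escalation. Membership can then depend on the event being counted. A participant may leave the set because a DLT stopped the dosing, and both the denominator and the DLT count shrink.

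The case is foreseeable. Section 2.3 says that the sentinel participant is an additional risk mitigation "measure to monitor infusion-related reactions and other early onset study treatment-related AEs". A severe reaction during the first infusion is the kind of event that leaves a planned dose incomplete.

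At stake is whether the set named for the SMC's decision shows the same counts as the rules the SMC is asked to apply.

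**Working it through.** **Step 1. What the planned dose can mean.** Section 3.5.7 does not define it. Three readings are possible:

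- A: the assigned dose level. Table 3-2 labels the planned groups by mg.
- B: a complete infusion at that level. Section 3.5.2 supports this: "The Safety Analysis Set (SS) consists of all study participants who receive at least 1 full or partial dose of study treatment". The SS therefore names partial dosing and the DES does not. Section 8.1 also computes the percentage of the planned dose received at each dosing visit.
- C: both Cycle 1 infusions, Days 1 and 15. Sections 2.3 and 8.1 also use the term for a single infusion, so this is less certain.

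**Step 2. The cases side by side (Part A).**

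| Participant | Section 2.3 | DES, A | DES, B | DES, C |
|---|---|---|---|---|
| DLT stops the first infusion; no further dose | DLT counts; not replaced | in | out | out |
| Full Day 1 infusion; DLT prevents Day 15 dose | DLT counts; not replaced | in | in | out |
| Both infusions complete; DLT afterwards | DLT counts | in | in | in |

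Reading B, which the SAP's own wording favours, conflicts with Section 2.3 in the first row. Reading C conflicts in the first two.

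In Part A1, Cohort 4 is the clearest case. It has one 120-minute infusion of 4000mg per 28-day cycle, so B and C coincide, and a DLT that stops that infusion takes the participant out.

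**Step 3. Worst-case size (Part A).** The plan gives no figure to reproduce. Let n be the number treated (3 to 6) and d the number with a DLT (at least 1). Assume that every DLT stops dosing, so that all d are outside the DES, and that all others complete the 28 days.

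- All-treated fraction without a DLT: (n − d)/n
- DES fraction without a DLT: (n − d)/(n − d)
- Escalation list (Section 2.3): 3/3, 4/4, 5/5, 5/6, 6/6

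The DES fraction is on the list whenever n − d ≥ 3.

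| n, d | All treated | On list? | DES | On list? | Section 2.3 DLT-count rule |
|---|---|---|---|---|---|
| 3, 1 | 2/3 | no | 2/2 | no | enroll up to 6 |
| 4, 1 | 3/4 | no | 3/3 | yes | enroll up to 6 |
| 5, 1 | 4/5 | no | 4/4 | yes | enroll up to 6 |
| 5, 2 | 3/5 | no | 3/3 | yes | 2 or more DLTs |
| 6, 1 | 5/6 | yes | 5/5 | yes | already 6; may escalate |
| 6, 2 | 4/6 | no | 4/4 | yes | 2 or more DLTs |
| 6, 3 | 3/6 | no | 3/3 | yes | 2 or more DLTs |

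Every other combination with d ≥ 1 has n − d < 3, and neither fraction is on the list. The two disagree in five outcomes: (4,1), (5,1), (5,2), (6,2) and (6,3). In all five the DES looks the more favourable to escalation.

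**The case against.** **The phrase is open.** On reading A, a participant infused at the assigned level is in the DES even if the infusion was cut short, and the conflict disappears. This stands: it would be wrong to say that the participant is excluded on any reading. The contrast with the SS wording and the percentage in Section 8.1 favour reading B but do not settle the matter.

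**Replacement is not membership.** Section 2.3 says who is replaced, not who is in the DES, and a careful reader could infer from it that participants with DLTs are meant to count. That is probably the intent. It is also why the definition should say so.

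**The decision rules already protect against the error.** This is the strongest point, and it stands. The rules for one DLT and for two or more act on participants at the dose level and do not mention the DES. In each of the five outcomes one of them applies and points away from escalation. Section 4.5 has the SMC review all safety data, DLTs included, for every participant in the cohort, and the SMC makes the final decision. In Part A1 one or more DLTs in a cohort bring an ad hoc SMC meeting whatever the DES shows, and there are no escalation fractions. A reader might infer that DLTs would be hidden from the SMC, or that the five outcomes are wrong escalations waiting to happen. The SAP supports neither.

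**No reported result changes.** Section 5.1 says that the DES is not needed for the study report, and Section 8 bases safety tables on the SS. This also stands.

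**Other documents may settle it.** Section 13.2 of the Part A SAP says that the definition follows the latest protocol, and Section 4.5 leaves details to the SMC Charter. Neither was available for this review. Matching protocol wording would not remove the conflict inside the SAP.

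**Conclusion.** The definition is badly fixed and should be corrected, but the consequence is limited. On the most natural reading, it leaves out a participant whose infusion is stopped by a DLT. If both Cycle 1 infusions are meant, it also leaves out one whose DLT prevents the second. Either result conflicts with Section 2.3.

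The size is five discrepant outcomes in cohorts of 3 to 6, on the worst-case assumption that every DLT stops dosing. The share of DLTs that would do so is not in the documents, so no probability is attached. A probability of wrong escalation would also need the SMC to apply the fractions to the DES and ignore the DLT-count rules, which Section 2.3 does not allow. What remains is that the set named for the decision can show a smaller denominator and fewer DLTs than the rules it serves. Confidence is moderate, because the key phrase is undefined.

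**What to change.** In Section 3.5.7 of both SAPs, define the DES as participants who either

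1. receive the planned infusion(s) and complete the 28-day DLT Observation Period, or
2. experience a DLT in that period after any full or partial dose of UCB6114.

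In Part A, add that only participants who miss the second dose for reasons other than toxicity are excluded and replaced, with the 7-day limit of Section 2.3. State which infusions are meant, so that the planned dose no longer has three readings.

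Check the wording against the protocol and the SMC Charter, and align them if they carry the same gap. The cost is a short text change in two SAPs. It needs no extra data and changes no study report table.

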3.6 Treatment assignment and treatment groups

In Part A, it is planned that study participants will be dosed Q2W at ascending dose levels in 5 cohorts. Treatment groups will be defined by each cohort/dose level and will be presented in ascending order and labelled in the TFLs as illustrated in Table 3-2.

Table 3-2: Treatment Group Labels

Cohort/Dose Level	Planned Treatment Group Label
Cohort 1 (Dose Level 1)	UCB6114 100mg
Cohort 2 (Dose Level 2)	UCB6114 250mg
Cohort 3 (Dose Level 3)	UCB6114 500mg
Cohort 4 (Dose Level 4)	UCB6114 1000mg
Cohort 5 (Dose Level 5)	UCB6114 2000mg

Note that the actual dose levels and treatment group labels may change depending on whether dose escalation criteria are met. Further, additional cohorts/dose levels may be included based on emerging data.

Cohort/dose level will be referred to as ‘treatment group’ from this point onwards in the SAP and in the TFLs.

3.7 Center pooling strategy

Each study site will contribute to the summaries of data from Part A according to the number of evaluable participants recruited; no separate summaries for each site will be presented.

3.8 Coding dictionaries

Adverse events and medical history will be coded by UCB, using the latest available version of the Medical Dictionary for Regulatory Activities (MedDRA®) (Version 25.1 or higher). The National Cancer Institute Common Terminology Criteria for AEs (Version 5.0) (NCI CTCAE) dictionary will also be used by the investigator to assign CTCAE severity grades to each AE and will be merged with the clinical database to define a CTCAE code and term to be used in the summaries of TEAEs by maximum CTCAE severity grade.

Medications (including prior anti-cancer systemic therapies) will be coded according to the World Health Organization Drug Dictionary (WHODD) (Version SEP/2020). Medical procedures will not be coded.

The versions of the coding dictionaries used will be displayed in the relevant TFLs.

3.9 Changes to protocol-defined analyses

The following changes to the protocol have been incorporated into the SAP:

- Other safety data have not been defined as safety endpoints in the protocol, e.g. clinical laboratory data, vital signs, ECG, echocardiogram, ECOG performance status and physical examination. These have been listed in Section 2.2.1 of the SAP as ‘other safety endpoints’ to support the characterization of the safety profile of UCB6114 and to provide supporting evidence of any measurements that are deemed abnormal and clinically significant and reported as an AE.
- ECOG performance status is defined as an efficacy assessment in Section 8.6.2 of the protocol, however, it will also be assessed from a safety perspective in Part A. The SAP therefore includes ECOG performance status as both a safety endpoint (Section 2.2.1) and an exploratory efficacy endpoint (changes from Baseline during Part A in Section 2.2.3).
- Section 9.4.2.1 of the protocol does not explicitly define the analysis set to be used for the antitumor activity endpoints but defines the denominator as the number of treated participants, which matches the protocol definition for the SS in Section 9.1 of the protocol. The SAP has been written to clarify that the PPS will be the primary analysis set for the analysis of the antitumor activity endpoints ([Section 3.5.3](#)) and that the SS will be used for the sensitivity analysis ([Section 3.5.2](#)).

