3.4 Protocol deviations

Per ICH definition, important protocol deviations (IPDs) are a subset of protocol deviations that may significantly impact the completeness, accuracy, and/or reliability of the study data or that may significantly affect a participant's rights, safety, or well-being. The criteria for identifying potentially important protocol deviations will be defined within the IPD specifications document.

For Part A of this study, IPDs will be categorized as follows:

- Inclusion/exclusion criteria deviations
- Incorrect treatment or dose administered
- Procedural non-compliance
- Prohibited concomitant medication use (see Section 6.5.2 of the protocol)
- Withdrawal criteria deviation

All protocol deviations will be reviewed as part of the ongoing data cleaning process and Data Evaluation Meetings (DEMs), and decisions made on whether they should be considered important or not, and whether they warrant a participant's exclusion from an analysis set, or partial exclusion from an analysis due to being an IPD (e.g. prohibited concomitant medication use). Multiple DEMs will be scheduled prior to the final database lock for Part A, in line with regulatory safety reporting requirements, with the final one held after all data have been verified/coded/entered into the database.

More specifically, participants who have IPDs relating to dosing of study treatment (e.g. interrupted, discontinued and missed infusion, incomplete/incorrect dose administered, additional dose received, or infusions administered outside of the defined visit window) will be

reviewed at the DEM for potential exclusion of UCB6114 concentration data from the by-visit summaries at an individual visit or from the visit at which the dosing deviation was observed onwards.

Any protocol deviations that are considered related to coronavirus disease 2019 (COVID-19) will be reviewed on an ongoing basis in case they collectively or individually give reason to consider a protocol amendment (e.g. study design changes or changes to primary analysis methods etc.). To facilitate this ongoing review, protocol deviations will be categorized as ‘related to COVID-19’ within the Clinical Trial Management System (CTMS). The COVID-19-related IPDs will then be listed separately for review and discussion at the DEMs.

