3.5.3 Per-protocol Set (PPS)

The Per-protocol Set (PPS) consists of all study participants in the SS who do not have IPDs that may substantially affect antitumor activity. Potential exclusions will be reviewed at the DEMs and a final determination of the composition of this analysis set will be made prior to the final database lock for Part A1.

The PPS will be the primary analysis set for the analysis of the exploratory antitumor activity endpoints.

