10.1.2 Analysis of the antitumor activity endpoints

The analyses of the antitumor activity endpoints in Part A1 will be performed for the PPS. As a sensitivity analysis, all analyses will be repeated for the SS. All listings will be presented for the SS. Summaries and listings will be presented by treatment group.

All lesion assessment data recorded at Baseline (Screening) and during the Treatment Period (every 8 weeks from Day 1 of Cycle 1 [± 7 days]) will be listed separately for target lesions, non-

target lesions and new lesions. Each post-Baseline tumor assessment will be labelled as ‘Tumor Assessment 1, Tumor Assessment 2 etc. – see further details below). These listings will include lesion number and lesion type (nodal/non-nodal), location, method of assessment, dimension (or an indication that the lesion is too small to measure, for target lesions only) and lesion response evaluation (for non-target lesions at post-Baseline assessments). The listing for target lesions will also include the derived eCRF component data used for the determination of the overall target lesion response at each post-Baseline assessment (e.g. sum of all dimensions across target lesions and percentage change from Baseline in the sum). In addition, the overall response assessment for target lesions and non-target lesions, as determined by the investigator, will be listed for each post-Baseline tumor assessment (Tumor Assessment 1, Tumor Assessment 2 etc.) together with the presence of new lesions and the investigator's overall tumor response assessment.

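### The Part A SAP makes the Per-protocol Set primary for antitumor activity and calls this a clarification, although it reports the protocol's denominator as all treated participants

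*SAP*

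**What the plan says.** Section 3.9 of the Part A SAP, which lists changes to protocol-defined analyses, notes that the protocol does not explicitly name an analysis set for the antitumor endpoints. It adds that the protocol "defines the denominator as the number of treated participants, which matches the protocol definition for the SS in Section 9.1 of the protocol". The same bullet continues: "The SAP has been written to clarify that the PPS will be the primary analysis set for the analysis of the antitumor activity endpoints". The SS becomes the sensitivity set.

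Section 3.5.3 says that the PPS "consists of all study participants in the SS who do not have IPDs that may substantially affect antitumor activity". Exclusions are reviewed at data evaluation meetings, and "a final determination of the composition of this analysis set will be made prior to the final database lock for Part A". Section 3.4 gives the IPD categories, among them incorrect treatment or dose, prohibited concomitant medication and "Withdrawal criteria deviation". Section 7 sends dosing deviations to the same meetings to be assessed for their effect on the PPS.

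Section 10.1.2 runs the antitumor analyses on the PPS, with every participant in the analysis set in the ORR and DCR denominator, and repeats them on the SS.

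The Part A1 SAP makes the same choice: "The analyses of the antitumor activity endpoints in Part A1 will be performed for the PPS". Its Section 3.9 does not mention it.

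**The concern.** A denominator of all treated participants cannot be clarified into a subset of them. By the SAP's own account, the primary ORR and DCR are now calculated on a different population from the one the protocol's denominator implies, and no reason is given.

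The subset is defined by deviations that mostly arise after treatment starts, and they are chosen because they may bear on the endpoint itself. Section 2.3 describes the study as open-label and nonrandomized, and investigators record tumor responses as the study goes along. Section 3.4 places the final data evaluation meeting after all data are in the database, so the responses are available when membership is decided. The primary rate then depends partly on case-by-case judgments made with outcomes in view, and in cohorts this small a single judgment is visible in the result.

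**Working it through.** **Inputs.** All are from the Part A SAP unless noted.
- Cohort size: 3 to 6 evaluable participants (Section 2.3).
- Maximum for Part A: 42, from 5 planned dose levels plus 1 added, and on average one additional participant (Section 2.4).
- ORR and DCR denominator: everyone in the analysis set used (Section 10.1.2).
- Interval: Clopper-Pearson, 95% (Section 10.1.2).
- Part A1 cohort size: up to 8 (Part A1 SAP, Section 2.3).
- Numbers of responders and of exclusions: not in the document, so assumed below.

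**The plan's own figure.** 6 dose levels × (6 + 1) = 42, which reproduces the stated maximum. Using the minimum of 3 gives 6 × (3 + 1) = 24, so 42 rests on full cohorts of 6. The choice of analysis set does not alter this figure.

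**Effect of the set on a rate.** Let n be the number treated, x the responders, a the excluded responders and b the excluded non-responders. The SS rate is x/n. The PPS rate is (x − a)/(n − a − b).

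| Case | SS rate | PPS rate |
|---|---|---|
| n = 6, x = 1, b = 1 | 1/6 = 16.7% (0.4 to 64.1) | 1/5 = 20.0% (0.5 to 71.6) |
| n = 6, x = 1, b = 2 | 1/6 = 16.7% (0.4 to 64.1) | 1/4 = 25.0% (0.6 to 80.6) |
| n = 6, x = 1, a = 1 | 1/6 = 16.7% | 0/5 = 0% |
| n = 6, x = 0, b = 1 | 0/6 = 0% | 0/5 = 0% |
| n = 8 (Part A1), x = 1, b = 1 | 1/8 = 12.5% | 1/7 = 14.3% |
| n = 8 (Part A1), x = 1, b = 2 | 1/8 = 12.5% | 1/6 = 16.7% |

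In the first row the shift is 20.0 − 16.7 = 3.3 percentage points.

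**Pooled illustration.** Take 42 treated, an assumed 12 with disease control, and excluded participants all without it. The SS gives 12/42 = 28.6% (15.7 to 44.6). The PPS gives 12/40 = 30.0% after 2 exclusions, 12/38 = 31.6% after 4 and 12/34 = 35.3% after 8.

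**Is the PPS needed to deal with later anti-cancer therapy?** Section 10.1.1 already stops best overall response (BOR) assessment at subsequent anti-cancer therapy and censors PFS before it. It also gives a PFS rule for participants with no post-baseline scan. These cases do not require a reduced analysis set.

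**The case against.** The case for leaving the plan alone has real force. Antitumor activity is exploratory, no hypothesis test or decision rule in the document uses it, and the primary safety endpoints are reported on the SS. The change is declared, since it sits in the section on changes to the protocol, and only its description as a clarification is loose. Every antitumor analysis is repeated on the SS, and PPS exclusions are counted (Section 5.2) and listed (Section 5.1). The all-treated result will be available, and the dispute is over which table is labelled primary. The intervals above are also far wider than the shift from one exclusion. All of this stands and limits the weight of the point.

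Four stronger readings are tempting, and the document does not support them.
- **That the PPS inflates ORR and DCR and lengthens PFS.** Stopping for progression or unacceptable toxicity is planned conduct, so early failures are not removed merely for failing. The criteria for identifying potentially important deviations are in a separate specification that is not shown. Excluding a responder lowers the rate.
- **That missed, interrupted or discontinued infusions lead to removal from the PPS.** That list in Section 3.4 concerns drug concentration data. Section 7 allows dosing deviations to be assessed for the PPS, but no stated rule removes them.
- **That PFS, DOR and OS depart from a protocol-defined population.** Section 3.9 reports only a denominator, which concerns rates.
- **That Part A1 departs from its protocol without saying so.** Part A follows protocol amendment 5 and Part A1 follows amendment 6. What amendment 6 says on this point cannot be checked, so the silence of the Part A1 Section 3.9 is not shown to be an error.

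**Conclusion.** The point holds for Part A, with modest weight. The SAP states the protocol's denominator, replaces it with a subset and calls that a clarification. The primary ORR and DCR then depend on case-by-case exclusions that can be made with responses visible.

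The illustrative size is 16.7% against 20.0% for one responder in a cohort of 6 with one non-responder excluded, and 25.0% with two excluded. This assumes one responder and one or two exclusions, all non-responders. Neither the number of exclusions nor the direction of any bias can be derived from the document. For Part A1 the argument rests only on avoiding post-baseline exclusions made with outcomes known, not on a conflict with its protocol.

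**What to change.** In the Part A SAP, Sections 3.5.2, 3.5.3, 4.8 and 10.1.2, make the SS the primary set for the antitumor endpoints and the PPS the sensitivity set. In Section 3.9, remove the bullet or reword it so that it no longer presents the PPS choice as a clarification. If the sponsor prefers to keep the PPS primary, Section 3.9 should call it a change of population, give the reason and list the PPS exclusion criteria in advance.

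The same swap is advisable in the Part A1 SAP (Sections 3.5.2, 3.5.3, 4.10 and 10.1.2).

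Both sets of outputs are already planned, so the cost is wording and table order. The primary rates may come out slightly less favourable.
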